8.3.5 ADVERSE EVENT REPORTING

See 8.3.1, 8.3.3.2, and 8.3.4 above

8.3.6 SERIOUS ADVERSE EVENT REPORTING

See 8.3.1, 8.3.3.2, and 8.3.4 above

8.3.7 REPORTING EVENTS TO PARTICIPANTS

See 8.3.1, 8.3.3.2, and 8.3.4 above

8.3.8 EVENTS OF SPECIAL INTEREST

N/A

8.3.9 REPORTING OF PREGNANCY

If a woman becomes pregnant while she is in the study she will be withdrawn and follow-up ensured with her health care provider.

8.4 UNANTICIPATED PROBLEMS

8.4.1 DEFINITION OF UNANTICIPATED PROBLEMS

See 8.3.1, 8.3.3.2, and 8.3.4 above.

8.4.2 UNANTICIPATED PROBLEMS REPORTING

See 8.3.1, 8.3.3.2, and 8.3.4 above.

8.4.3 REPORTING UNANTICIPATED PROBLEMS TO PARTICIPANTS

N/A

9 STATISTICAL CONSIDERATIONS

9.1 STATISTICAL HYPOTHESES

Aim 1: To examine the feasibility of the multi-component behavioral intervention. We will assess enrollment and retention rates; barriers and facilitators to enrollment; intervention fidelity; suitability of study procedures and outcome measures; and participant satisfaction with the intervention and study protocol.

Aim 2: To evaluate the initial efficacy of the intervention by comparing an intervention group to a wait-list control group (n=80; 40 per group) in a pilot study to a) decrease the primary outcomes of biologic CVD risk factors (blood pressure [BP], arterial stiffness, lipids, blood glucose); b) improve secondary outcomes (health behaviors: nutrition, physical activity, sleep, coping strategies) and other biological factors related to CVD risk (adiposity, inflammatory and stress biomarkers, vasomotor symptoms) from Time 1 (baseline) to Time 2 (6 months) and Time 3 (12 months).

Hypotheses and Statistical Considerations: This pilot study will descriptively assess the feasibility and validity of the cluster randomized controlled trial plan and is not expected to test the hypotheses of the main clinical trial.

We expect that on average, the intervention group will have a slower progression or a decrease in BP, arterial stiffness, lipids, and blood glucose compared to the wait-list control from Time 1 (baseline) to Time 2 (6 months) and Time 3 (12 months).

We expect the intervention group will show improvements in health behaviors (nutrition, physical activity, sleep, coping strategies, self-efficacy), adiposity, inflammatory and stress biomarkers, and vasomotor symptoms from Time 1 (baseline) to Time 2 (6 months) and Time 3 (12 months).

9.2 SAMPLE SIZE DETERMINATION

Sample size will be limited by available resources. Prior clinical trials among Latinas in North Carolina have enrolled 80-184 women successfully with <20% attrition [45]; therefore, enrollment of 80 women is realistic and achievable. Prior interventions in stress management [46] and exercise plus nutrition education [47] observed a change in systolic BP of 6mmHg (SD \pm 11); our sample of 80 participants will yield 70% power to detect a change this large. This pilot study is effectively a cluster-randomized trial with two groups. Because we have two groups, the pilot is not sufficient for the estimation of intraclass correlation of change in outcomes, so we do not use traditional analysis methods for cluster-randomized trials. We can however, use baseline data to estimate potential variability between clusters, which will be helpful in the estimation of the number of clusters/cluster size required for the fully-powered clinical trial.

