Disadvantaged neighborhoods have a high concentration of poverty and unemployment, which influences crime rates, availability of public services, parks, grocery stores, and fast food and liquor establishments [14]. Many Latinas live in neighborhoods with only 32% as many grocery stores as less disadvantaged communities and thus lack access to healthy food [15]. Living in disadvantaged and unsafe neighborhoods increases stress [16], limits physical activity and increases sedentary behavior [17,18], which influence biologic CVD risk factors such as blood pressure, cholesterol, adiposity and inflammation [19,20]. To address the built environment, our intervention will provide women with information on where to access healthy low-cost food and safe spaces for physical activity.

The most consistent behavioral factors contributing to CVD risk during perimenopause are inadequate nutrition, decreased physical activity [21], poor sleep patterns [22], and chronic stress [23]. Social cognitive theory [24] posits that enhancing an individual's knowledge and skills to perform a new behavior improves self-efficacy, which in turn increases likelihood that the new behavior will be maintained. National reports have shown that <16% of adult Latinas consume the recommended servings of whole grains, fruits, and vegetables [25]. The Hispanic Community Health Study/Study of Latinos has reported that only 27% of Latinas age 45-64 years meet the national guidelines for physical activity [26]. In addition, over half of perimenopausal Latinas report difficulty sleeping [27], which has been associated with arterial stiffness [28], a hardening of the vessel wall often predictive of CVD [29]. Latinas report higher levels of perceived stress compared to perimenopausal women of any other race/ethnicity in the US [30]. In this study, we will facilitate behavioral change and improve self-efficacy in perimenopausal Latinas by helping them acquire coping strategies for problem-solving, communication, stress management, and cognitive behavioral modification.

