2.3 RISK/BENEFIT ASSESSMENT

2.3.1 KNOWN POTENTIAL RISKS

Risks to Human Subjects

Institutional Review Board (IRB) approval was obtained from The University of North Carolina at Chapel Hill (UNC-CH). Using a cluster randomized two-group, repeated measures experimental design, the goal of the study is to investigate the feasibility and initial efficacy of a 12-month intervention consisting of: **Phase I**) 12-week nutrition and exercise education, physical activity group sessions, coping skills training, and stress management intervention in perimenopausal Latinas; **Phase II**) 6 months of continued monthly contact to help women improve health behaviors and self-efficacy; and **Phase III**) 6 months of health maintenance without contact from study staff. We will partner with community centers to enroll women and we will partner with two churches in two North Carolina counties to deliver the intervention.

Inclusion criteria include age 40-60 years; self-identify as Latina; understand spoken English or Spanish; perimenopausal (menstrual bleeding in the past three months, but timing of periods have varied in past year, or no menstrual bleeding in the past 3-11 months) or early postmenopausal (1-2 years since final menstrual period); intact uterus and at least one ovary; not currently pregnant; no hormone therapy or oral contraceptives in the past three months. Potential participants will fill out a health history questionnaire to ascertain if they have a history of CVD (heart attack, stroke, coronary heart disease), heart murmur, congenital heart disease, family history of sudden death, difficulty walking or exercising. Women who answers yes to any of these health history questions will be excluded from the study and referred to a health care provider. After enrollment and baseline assessment, two churches in two counties will be randomly assigned to either the intervention or control group. Participants will be assigned to the group in their respective county. Participants will be informed of their group assignment by telephone.

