Data will be collected at Time 1 (baseline [0 months]), Time 2 (post Intensive Intervention and Continued Support [6 months]), and Time 3 (6 months after completion of Continued Support [12 months]). Data collected will include the primary outcomes of blood pressure, arterial stiffness based on carotid-femoral pulse wave velocity measures, lipid profile (total cholesterol, high-density lipoprotein, low-density lipoprotein, triglycerides), blood glucose; secondary outcomes of health behaviors (Sleep Quality Questionnaire, Food Behavior Checklist, Physical Activity Questionnaire, and 7-day Accelerometer), self-efficacy (Eating Self-Efficacy Scale and Exercise Self-Efficacy Scale), body mass index, waist circumference, hs-CRP, hair cortisol, and vasomotor symptoms. We will also evaluate the feasibility of the study including, number of eligible participants; methods of identifying/recruiting participants; willingness of participants to be randomized; practicality of delivering the intervention in the proposed setting; enrollment and retention rates, and suitability of the intervention and assessment protocol. Data analysis will use descriptive statistics and general linear mixed models to test the hypotheses. Both intervention and control group participants will each receive \$120 for their time during data collection visits (\$35 at Time 1, \$40 at Time 2, \$45 at Time 3) and \$5 to help with transportation costs each time they come to class or data collection visit.

Participants in the intervention group will receive a 12-week Intensive Intervention (Phase I) with weekly 2-hour sessions consisting of 60 minutes of nutrition and exercise education and coping skills training, a 45-minute physical activity class, and 15-minute stress management session. During Continued Support (Phase II), participants will meet monthly for 3 months for 60 minutes of classroom discussion regarding problems they are having with nutrition and physical activity. Data collection in the wait-list control group will occur at the same time intervals as women in the intervention group. Following the last data collection, we will offer Phase I of the intervention to women in the wait-list control group.

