6.3 MEASURES TO MINIMIZE BIAS: RANDOMIZATION AND BLINDING

After enrollment and baseline assessment, the two churches will be randomized to either the intervention or wait-list control group using a computer-generated randomization table. Participants will be informed of their group assignment by telephone. Data collection research assistants will be blinded to group status.

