9.3 POPULATIONS FOR ANALYSES

Means, standard deviations, minimums, medians, and maximums will be determined for each continuous variable; frequencies and percentages will be tabulated for each categorical variable. Preliminary analyses will be performed to determine whether, despite randomization, the intervention and control groups were unbalanced on age, education, income, or other participant characteristics. Any variable with an imbalance between the groups at baseline will be examined to determine whether it is related to any of the outcome variables. If significant relationships are identified, the variable will be included as a covariate in the models for the affected outcome(s) as a potential confounder. An intent-to-treat analysis will be used in which all subjects are included in the analysis and analyzed according to their initial randomized assignment.

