9.4 STATISTICAL ANALYSES

9.4.1 GENERAL APPROACH

Aim 1. Using descriptive statistics (e.g., frequency, percentage, means, SDs), we will summarize enrollment and retention rates, and proportion of intervention sessions the participants attended. We will measure fidelity of the intervention ($\geq 80\%$ attendance; delivery of $>80\%$ of content) using the process evaluation guide, and assess participant satisfaction with the study and the intervention using the exit interview.

Aim 2. We will use an intent-to-treat approach. Because random assignment is by group and not individually, we will examine potential systematic differences closely between the two groups, comparing baseline characteristics using the Student's t-test or Mann-Whitney test for continuous variables and Chi-square or Fisher's exact test for categorical variables. We will assess change in primary and secondary outcomes in the intervention and control group using the Student's t-test or Mann-Whitney test for continuous variables and Chi-square or Fisher's exact test for categorical variables.

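### The 70% power in section 9.2 holds only if the women are independent; with two churches randomised, one per arm, it is not the power of a valid test of the intervention, and the sentence should say so.

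*Combined protocol and SAP*

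**What the plan says.** Section 9.2 sets the sample size by available resources, cites a 6 mmHg change in systolic blood pressure (SD 11) from earlier interventions, and states that "our sample of 80 participants will yield 70% power to detect a change this large". It gives no test, alpha, sidedness, time point, ICC or design effect. It mentions attrition below 20% only to support the feasibility of enrolling 80 women. The same paragraph then says that the pilot is effectively cluster-randomised and that the ICC of change cannot be estimated, "so we do not use traditional analysis methods for cluster-randomized trials".

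Section 6.3 says that "the two churches will be randomized to either the intervention or wait-list control group". Section 9.4.1 says "We will assess change in primary and secondary outcomes in the intervention and control group using the Student's t-test or Mann-Whitney test", with chi-square or Fisher's exact tests for categorical outcomes. Section 9.1 describes the pilot as descriptive and not intended to test the main trial's hypotheses. However, section 3 places initial efficacy within the primary objective, and Aim 2 in 9.1 compares the two groups.

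**The concern.** A power statement says how often a test will detect a true effect of a given size, and it presupposes that the test has its nominal error rate. Here the figure treats 80 women as 80 independent units, while the randomisation supplies two units. If women at one church change together for any reason other than the intervention, an individual-level test counts that shared change as an intervention effect. An unqualified 70% invites a reader to take a significant between-arm p-value as evidence for the intervention, when it may reflect a difference between two churches. Because the basis is not stated, the reader also cannot tell how far the figure falls with attrition.

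**Working it through.** **Inputs.** Difference 6 mmHg and SD 11 (9.2); 80 women, 40 per arm (9.1); two churches, one per arm (6.3); t or Mann-Whitney test on change (9.4.1); 20% as the attrition ceiling (5.5), giving 64 completers, 32 per arm. Assumptions: alpha 0.05; 6 mmHg is the between-group difference in change; 11 is the SD of change.

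**1. The plan's figure, with independent women.** SE = 11 × √(2/n).
- n = 40: SE = 2.460 and 6/2.460 = 2.439. Two-sided power is Φ(2.439 − 1.960) = 68.4% by the normal approximation and 67.3% by the noncentral t.
- n = 32: SE = 2.750 and 6/2.750 = 2.182. Power is 58.8% (normal) or 57.5% (t).

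So 70% is a fair rounding of the calculation with all 80 women. A within-group reading does not fit: a paired t-test would have 92.0% power with 40 women and 99.8% with 80.

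**2. What the design leaves for a test of the intervention.** Degrees of freedom for between-church variance = 2 churches − 2 arms = 0. Between-church variance therefore cannot be estimated separately from the intervention effect, whichever model is fitted. The mixed models named in 2.3.1 and the covariates in 9.3 do not change this.

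**3. Error rate of the planned t-test.** Let ρ be the ICC of change and m the women per arm. The true variance of the arm difference is (2 × 11²/m) × (1 + (m − 1)ρ). The t-test estimates (2 × 11²/m) × (1 − ρ). With no intervention effect, its statistic is therefore k times a t variable on 2m − 2 df, with k = √[(1 + (m − 1)ρ)/(1 − ρ)], and the type I error is P(|t| > t_crit/k). With m = 40, t_crit = 1.991 on 78 df. Example at ρ = 0.01: k = √(1.39/0.99) = 1.185; 1.991/1.185 = 1.680; P(|t| > 1.680) = 9.7%.

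| Assumed ρ | Design effect, m = 40 | Type I error, 40 per arm | Type I error, 32 per arm |
|---|---|---|---|
| 0 | 1 | 5.0% | 5.0% |
| 0.005 | 1.195 | 7.3% | 6.8% |
| 0.01 | 1.39 | 9.7% | 8.7% |
| 0.02 | 1.78 | 14.4% | 12.5% |
| 0.05 | 2.95 | 26.2% | 22.7% |

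A simulation of 40,000 trials per setting with 40 per arm gave 9.8% at ρ = 0.01 and 25.9% at ρ = 0.05.

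**4. Precision, all t-based.** The 95% half-width with independent women is 1.991 × 2.460 = 4.9 mmHg with 80 and 1.999 × 2.750 = 5.5 mmHg with 64. With 80 women and ρ treated as known, SE = 2.460 × √(design effect) = 2.689 / 2.900 / 3.282 / 4.225 at ρ = 0.005 / 0.01 / 0.02 / 0.05. Multiplying by 1.991 gives half-widths of about 5.4 / 5.8 / 6.5 / 8.4 mmHg.

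**The case against.** The strongest reply is that the plan already concedes the point. Section 9.2 names the clustering straight after the power sentence and leaves adequate power to a later trial, 9.1 calls the pilot descriptive, and 9.4.1 plans closer baseline comparisons because assignment is by group. This stands as mitigation: n=80 comes from resources, so no design decision rests on the 70%. It does not settle the matter. None of these statements qualifies the figure, and being unable to estimate the ICC does not make an individual-level test valid.

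Four stronger readings are tempting, and the documents do not support them.

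- *The arithmetic is wrong.* It is not; under independence 70% is a fair rounding.
- *The plan's own background shows that change is clustered.* Section 2.2 speaks of neighbourhood conditions "which influence biologic CVD risk factors such as blood pressure, cholesterol, adiposity and inflammation". That concerns levels, and change from baseline removes stable differences in level. The ICC of change is unknown, which is why a range is shown.
- *County is fully confounded with arm.* Section 2.3.1 says "Participants will be assigned to the group in their respective county" and, like 5.5, works with two counties, but the synopsis lists five. County confounding is therefore unsettled. Church and arm are confounded either way.
- *The 70% already allows for attrition.* A one-sided 5% test with 64 completers does give 69.6% to 70.4%. No section states a one-sided test, 9.2 ties the figure to 80 participants, and 20% is a ceiling. That reading is speculative.

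**Conclusion.** The 70% is correct to rounding as a calculation for independent women, and as written it claims a property that the design does not have. With one church per arm, no valid test of the intervention can be built from the trial data alone without assuming an ICC, so there is no single corrected power to put in its place. That conclusion rests only on the randomisation scheme.

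The size of the error inflation does depend on assumption: about 7% to 26% two-sided with 40 per arm, for ICCs of change from 0.005 to 0.05. The independent-women figures rest on reading 6 mmHg and SD 11 as a between-group difference in change and its SD, at two-sided 5%. That reading fits the 70% best, but it is an inference. The sentence should be corrected; the point does not call for a redesign or a larger pilot.

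**What to change.** In 9.2, replace the power sentence as follows.

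- Give a figure labelled as assuming independent women, with the test, alpha, sidedness, evaluable number and time point (6 or 12 months). Say whether 6 mmHg and 11 are the between-group difference in change and the SD of change. If so, and if two-sided 5%, the t-based figures are about 67% with 80 completers and 57% with 64.
- State that, with one church per arm, no power is claimed for the intervention effect, and that between-arm p-values and confidence intervals are descriptive and cannot separate the intervention from the church. Refer to 9.1.
- Justify n=80 by feasibility and by the individual-level half-widths above. Mark any clustered values as resting on assumed ICCs.

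The cost is one paragraph, a less favourable stated figure and a more cautious reading of the p-values. Enrolment does not change.

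A separate inconsistency should be reconciled at the same time: 2.3.1 plans "general linear mixed models to test the hypotheses", whereas 9.4.1 plans t or Mann-Whitney tests. Resolving it would not by itself cure the power statement.

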9.3 POPULATIONS FOR ANALYSES

Means, standard deviations, minimums, medians, and maximums will be determined for each continuous variable; frequencies and percentages will be tabulated for each categorical variable. Preliminary analyses will be performed to determine whether, despite randomization, the intervention and control groups were unbalanced on age, education, income, or other participant characteristics. Any variable with an imbalance between the groups at baseline will be examined to determine whether it is related to any of the outcome variables. If significant relationships are identified, the variable will be included as a covariate in the models for the affected outcome(s) as a potential confounder. An intent-to-treat analysis will be used in which all subjects are included in the analysis and analyzed according to their initial randomized assignment.

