1.3 SCHEDULE OF ACTIVITIES

Summary of Variables, Measurement, and Data Collection Time Points			
Variables and Measurement	0	6	12
Feasibility			
*Process evaluation checklist (bi-monthly)	--	--	--
*Screening and enrollment logs	X	X	X
*Intervention attendance	X	X	X
*Data collection attendance	X	X	X
Exit interview			X
Biological CVD Risk Factors (Primary Outcomes)			
Systolic and diastolic blood pressure	X	X	X
Fasting blood glucose	X		X
Fasting lipid profile	X		X
Arterial stiffness (carotid-femoral PWV)	X		X
	X		X
Health Behavior (Secondary Outcomes)			
Nutrition and food security	X	X	X
Physical activity questionnaire	X	X	X
Accelerometer (7 days, 24 hours/day)	X	X	X
Sleep questionnaire	X	X	X
Perceived stress	X	X	X
Coping response inventory	X	X	X
Eating self-efficacy scale	X	X	X
Exercise self-efficacy scale	X	X	X
Biological Influences (Secondary Outcomes)			
Height, Weight, BMI	X	X	X
Waist Circumference	X	X	X
Hair Cortisol and Hs-CRP	X		X
Vasomotor symptoms questionnaire	X	X	X
Demographic, Sociocultural, and Environmental			
Demographic questionnaire (e.g., age, education)	X	X	X
Acculturation questionnaire (e.g., years in US)			
Everyday discrimination scale			
Brief resilience scale			
Health history questionnaire			
Reproductive history questionnaire			
Community food assessment			
Neighborhood risk assessment			
Physical activity resource assessment			

0 = baseline; 6 = 6-month (completion of intensive intervention and continued support); 12 = 12-month (after 6 months of maintenance on own); BMI = body mass index; Hs-CRP = high-sensitivity C-reactive protein; PWV = pulse wave velocity

*Completed by Project Manager

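### Covariate adjustment in 9.3 depends on observed imbalance and then on significance, so the covariate set is data-driven, differs by outcome, and leaves bias and precision on the table that a pre-fixed core list would recover

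*Combined protocol and SAP*

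**What the plan says.** Section 9.3 checks the groups for imbalance on age, education and income, and leaves the list open to other participant characteristics. Then: "Any variable with an imbalance between the groups at baseline will be examined" for a relation with any of the outcomes. The last step is: "If significant relationships are identified, the variable will be included as a covariate in the models for the affected outcome(s). The section gives no threshold for imbalance, no significance level for the relation with outcome, and no list of covariates that always enter.

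Section 9.4.1 gives the reason for looking: "Because random assignment is by group and not individually, we will examine potential systematic differences closely between the two groups". For the baseline comparison it names the t-test or Mann-Whitney test and the chi-square or Fisher's exact test. It then compares change in the outcomes with the same two-sample tests, which hold no covariate. Section 2.3.1 instead mentions general linear mixed models. The models to which 9.3 would add covariates are therefore not defined.

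On the design, section 6.3 says that "the two churches will be randomized to either the intervention or wait-list control group", and section 2.3.1 assigns women according to their county. Each arm is one church.

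**The concern.** With one church per arm, real differences between the groups should be expected, and 9.4.1 says as much. A rule that adjusts only after a variable passes two screens has three weaknesses here.

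- At 40 per arm, a non-significant baseline test is weak evidence of balance. Moderate differences that go undetected stay in the estimate.
- When the groups happen to be balanced, prognostic baseline variables almost never enter, and the precision they offer is lost.
- Each outcome can end with its own covariate set, chosen after the data are seen. The effect estimates across outcomes are then harder to compare and to carry into the larger trial.

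Section 9.1 (Aim 2) asks the pilot for an estimate of initial efficacy, so the quality of that estimate matters even though the pilot is not meant to be confirmatory.

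**Working it through.** **Inputs.** From 9.1: "n=80; 40 per group". From 9.2: "observed a change in systolic BP of 6mmHg" with SD 11, read as a between-group difference in change. Assumed, because the plan does not say: two-sided 5% for both screens, a t-test for imbalance, one normally distributed covariate, no dropout and no church effect.

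**1. The plan's own figure.** Section 9.2 states: "our sample of 80 participants will yield 70% power to detect a change this large". The standardized effect is 6/11 = 0.545. The normal approximation gives Φ(0.545 × √(40/2) − 1.96) = Φ(0.479) = 68.4%; the noncentral t gives 67.3%. The stated 70% is reproduced to within about two points on the normal approximation, so the inputs are read as intended.

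**2. First screen (imbalance).** Significance needs an observed standardized difference of t(0.975; 78 df) × √(2/40) = 0.445. Noncentral-t power with noncentrality d√20:

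| True difference d (SD) | Detected | Missed |
|---|---|---|
| 0.3 | 26% | 74% |
| 0.4 | 42% | 58% |
| 0.5 | 60% | 40% |

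**3. Second screen (relation with outcome).** With 80 women, a correlation of 0.3 is significant about 78% of the time. For d = 0.3 to 0.5 and r = 0.3, a genuine confounder passes both screens in only 22% to 48% of simulated trials.

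**4. Bias left by the rule.** Simulation with 20,000 runs per setting, 40 per arm and no true effect. Mean bias is in SD of change; the unadjusted value is d × r.

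| d | r | Unadjusted | Rule in 9.3 | Covariate fixed in advance |
|---|---|---|---|---|
| 0.4 | 0.3 | 0.12 | 0.05 | about 0 |
| 0.4 | 0.5 | 0.20 | 0.07 | about 0 |

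In mmHg the rule leaves 0.051 × 11 = 0.56 to 0.072 × 11 = 0.79, so about 0.6 to 0.8. Across d = 0.3 to 0.5 the range is 0.05 to 0.07 SD. Rejection at nominal 5% is about 5% to 6% under the rule.

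**5. Precision when the groups are balanced.** A covariate with correlation r reduces the residual SD to 11√(1 − r²): 10.49 at r = 0.3 and 9.53 at r = 0.5. The standardized effects become 6/10.49 = 0.572 and 6/9.53 = 0.630, and noncentral-t power (77 df) is 71% and 79%. Under the rule the covariate enters in only about 4% to 5% of such trials, so power stays at about 67%.

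**6. Cost of adjusting for a variable aligned with arm.** With equal arms, the variance of the arm effect is multiplied by 1 + d²/4. At the detection threshold this is 1 + 0.445²/4 = 1.05; at d = 1 it is 1.25; a factor of 5 needs d = 4.

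**The case against.** The strongest reply has five parts.

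*The first screen may not be a significance test.* Section 9.3 speaks only of imbalance, and 9.4.1 does not say that its tests drive the choice of covariates. This stands: the miss rates in step 2 are conditional on that reading. If imbalance is judged some other way, the criterion is unstated and the rule is undefined, which the same fix cures.

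*The rule helps.* This also stands. At d = 0.4 it removes more than half of the unadjusted bias.

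*A reader might infer that a fixed list is better in every respect.* The documents and the calculation do not support that. The near-zero bias in step 4 arises because the fixed list contains the confounder. If the imbalanced variable is off the list and unrelated to what is on it, bias at d = 0.4 returns to 0.12 to 0.20 SD, worse than the 0.05 to 0.07 SD under the rule. The data-driven check should therefore be kept in a secondary place.

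*A reader might also infer that the rule favours variables nearly collinear with arm.* That goes too far. Selection does rise with association with arm, but a variable that just passes the first screen costs 5% in variance. Place-level measures such as the "Neighborhood risk assessment" appear in the schedule (1.3), but no section names them as covariates, and 4.3 says that environmental data serve to tailor the intervention. The sections also differ on whether recruitment covers two counties (5.5) or five (1.1), so a score that is constant within an arm is not established.

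*The effect is small and this is a pilot.* A bias of 0.6 to 0.8 mmHg compares with an unadjusted 95% half-width of 1.99 × 11 × √(2/40) = 4.9 mmHg, and 9.1 disclaims testing the main-trial hypotheses. This lowers the importance. It does not justify outcome-specific covariates chosen after the fact when baseline data already collected allow a better estimate.

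**Conclusion.** The concern holds in a limited form. The rule in 9.3 makes adjustment depend on the data, outcome by outcome, without a stated imbalance criterion or alpha. Assuming 5% tests and 40 per arm, it misses 0.3 to 0.5 SD imbalances 74% to 40% of the time. It leaves about 0.6 to 0.8 mmHg of bias at d = 0.4 and r = 0.3 to 0.5. With balanced groups it forgoes roughly 4 to 12 percentage points of power for a 6 mmHg effect. Type I error for a measured confounder is close to nominal, and the rule is better than no adjustment.

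The values of d and r are assumptions, since the documents give neither. The simulations contain no church effect. With one church per arm, that effect is fully confounded with the intervention whatever covariates are used. This is a change worth making before analysis, not a threat to the pilot's validity beyond what its two-cluster design already imposes.

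**What to change.** In 9.3 and 9.4.1:

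- Name a linear, ANCOVA-type model for continuous outcomes, and reconcile it with the two-sample tests in 9.4.1 and the mixed models mentioned in 2.3.1.
- Always include a short core list, the same for every outcome whatever the baseline comparison shows: the outcome's baseline value, age, relevant baseline medication use (5.2 admits women on antihypertensive, lipid-lowering or diabetes medication), and education and income, which 9.3 already names.
- Fix the list before any outcome data are examined, which means before the 6-month analysis in 9.4.6. Unblinding is not a usable milestone, because 6.3 blinds only the data collectors.
- Show baseline comparability as standardized differences rather than p-values.
- Keep adjustment for other imbalanced participant characteristics as a labelled sensitivity analysis, with its imbalance criterion stated.
- Report church-, county- and neighborhood-level measures descriptively only, since place coincides with arm, and state that no covariate list separates the intervention effect from the church effect.

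The cost is some SAP wording and a few degrees of freedom. With one term each, five covariates take the residual from 78 to 73 with 80 women, or from 62 to 57 if 20% are lost (32 per arm). Categorical coding of education or income would use somewhat more.
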